## WHO RISK CATEGORIES

Risk group	Shipping Requirement	Pathogen	Risk to individuals	Risk to the community	Examples of Pathogens and their Risk groups
1	Standard Diagnostic (IATA PI650)	A micro-organism that is unlikely to cause human disease.	NONE OR VERY LOW	NONE OR VERY LOW	Most bacteria, fungi and viruses
2	Standard Diagnostic (IATA PI650)	A pathogen that can cause human or animal disease but is unlikely to be a serious hazard to laboratory workers, the community, livestock or the environment. Laboratory exposures may cause serious infection, but effective treatment and preventive measures are available and the risk of spread of infection is limited.	MODERATE	LOW	Legionella pneumophila E. Coli 0157
3	Standard Diagnostic (IATA PI650)	A pathogen that usually causes serious human or animal disease but does not ordinarily spread from one infected individual to another. Effective treatment and preventive measures are available.	HIGH	LOW	HIV Hepatitis B Hepatitis C
4	High risk (IATA PI602)	A pathogen that usually causes serious human or animal disease and that can be readily transmitted from one individual to another, directly or indirectly. Effective treatment and preventive measures are not usually available.	HIGH	HIGH	Lassa Fever Ebola Virus

If a subject is being withdrawn due to a suspected infection in WHO risk categories 2, 3 and 4 no biological samples from this subject are allowed to be sent to the laboratory. Samples will be destroyed according to normal routines at the study site.

---

## **NEW YORK HEART ASSOCIATION (NYHA) CLASSIFICATION**

The NYHA classification will be based on the following definitions:

Class I           No limitation:

Ordinary physical exercise does not cause undue fatigue, dyspnoea or palpitations.

Class II           Slight limitation of physical activity:

Comfortable at rest but ordinary activity results in fatigue, palpitations, dyspnoea.

Class III          Marked limitation of physical activity:

Comfortable at rest but less than ordinary activity results in symptoms.

Class IV          Unable to carry out any physical activity without discomfort:

Symptoms of congestive heart failure are present even at rest with increased discomfort with any physical activity.

---

## **EUROQOL (EQ-5D)**

### **Health Questionnaire** *English version for the UK*

By placing a tick in one box in each group below, please indicate which statements best describe your own health state today.

**Mobility**

I have no problems in walking about

I have some problems in walking about

I am confined to bed

**Self-Care**

I have no problems with self-care

I have some problems washing or dressing myself

I am unable to wash or dress myself

**Usual Activities** (e.g. work, study, housework, family or leisure activities)

I have no problems with performing my usual activities

I have some problems with performing my usual activities

I am unable to perform my usual activities

**Pain/Discomfort**

I have no pain or discomfort

I have moderate pain or discomfort

I have extreme pain or discomfort

**Anxiety/Depression**

I am not anxious or depressed

I am moderately anxious or depressed

I am extremely anxious or depressed

To help people say how good or bad a health state is, we have drawn a scale (rather like a thermometer) on which the best state you can imagine is marked 100 and the worst state you can imagine is marked 0.

We would like you to indicate on this scale how good or bad your own health is today, in your opinion. Please do this by drawing a line from the box below to whichever point on the scale indicates how good or bad your health state is today.

Health Questionnaire

English version for the UK

Best  
imaginable  
health state

100

90

80

70

60

50

40

30

20

10

0

Worst  
imaginable  
health state

---

## ALGORITHM ON MANAGEMENT OF HYPONATRAEMIA

If a patient experiences a serum sodium  $\leq 125$  mmol/L, with or without symptoms, dosing of blinded investigational product will be interrupted. A repeat serum sodium concentration will be drawn within 3 days of the receipt of the result.

- If the repeat sodium concentration within 3 days is  $\geq 130$  mmol/L

Investigational product may be restarted unless otherwise contraindicated. Serum sodium will be rechecked in 7 days after restarting the investigational product.

- If the repeat sodium concentration within 7 days of restarting the investigational product is  $< 130$  mmol/L, investigational product will be discontinued. Patients will have an end of treatment visit and a follow-up visit three weeks after discontinuation of investigational product as specified in section 5.8.1 in the CSP.
- If the repeat sodium concentration within 7 days of restarting the investigational product is  $\geq 130$  mmol/L, further management should be based on composite of sodium concentration, clinical assessment of the patient and an evaluation of underlying cause of hyponatraemia.

- If the repeat sodium concentration within 3 days is  $< 130$  mmol/L

If there is **no** suspected new, temporary, and reversible cause of hyponatraemia based on clinical assessment (other than investigational product), investigational product will be discontinued. Patients will have an end of treatment visit and a follow-up visit three weeks after discontinuation of investigational product as specified in section 5.8.1 in the CSP.

If there is a suspected new, temporary, and reversible cause of hyponatraemia based on clinical assessment (other than investigational product), investigational product will continue to be interrupted. The suspected cause of hyponatraemia should be identified and corrected. The serum sodium will be rechecked in another 7 days.

- If the repeat sodium concentration within 7 days is  $< 130$  mmol/L, investigational product will be discontinued. Patients will have an end of treatment visit and a follow-up visit three weeks after discontinuation of investigational product as specified in section 5.8.1 in the CSP.

- If the repeat sodium level concentration within 7 days is  $\geq 130$  mmol/L investigational product may be restarted unless otherwise contraindicated. Serum sodium will be rechecked in 7 days after restarting the investigational product, and further management should be based on composite of sodium concentration, clinical assessment of the patient and an evaluation of underlying cause of hyponatraemia.

For patients whose serum sodium is in the range of 126-129 mmol/L, the investigator's clinical judgment should apply concerning whether such patients should be entered into this algorithm.

---

## ALGORITHM ON MANAGEMENT OF SUSTAINED ELEVATED LIVER SAFETY ABNORMALITIES

The monitoring for liver safety will be performed using the serum levels of AST, ALT and TB (see [Figure 1](#) algorithm flow chart).

**Patients with a central laboratory ALT and/or AST >3 X ULN** will be scheduled for a follow-up visit within 3 days following receipt of the initial laboratory results, to obtain repeat central laboratory ALT, AST, TB and Alkaline Phosphatase (ALK-P). In the event that the repeat laboratory assessments cannot be obtained within 3 days, the Investigator is encouraged to discuss possible alternatives with the Sponsor. Patients should remain on study medication until confirmatory results are obtained, unless otherwise contraindicated.

- **If the repeat ALT and AST are  $\leq 3X$  ULN**, patient should continue double-blind treatment according to their original visit schedule unless otherwise contraindicated.
- **If the repeat ALT and/or AST are  $>3X$  ULN but  $\leq 8X$  ULN and TB  $\leq 1.5X$  ULN**, the patient's medical history, including details of risk factors for liver diseases, should be evaluated for potential underlying aetiologies. In addition, specialized blood sampling will be performed to evaluate liver function as well as identify potential causes of laboratory elevation(s). The Investigator should continue to monitor the patient's liver tests every 3 days following receipt of the prior laboratory results until the ALT and AST are  $\leq 2X$  ULN or until ALT and AST are at or below baseline levels. The frequency of retesting can decrease to once a week or less if abnormalities stabilize and the patient is asymptomatic. Patients should remain on study medication unless confirmatory results indicate that a criterion for discontinuation has been met or continuing study medication would be otherwise contraindicated.

**Patients must be discontinued from the study if an initial and repeat confirmatory laboratory tests meet any of the following criteria:**

- ALT and/or AST are  $>3$  x ULN and TB  $>1.5$  x ULN
- ALT and/or AST are  $>5$  x ULN for  $\geq 14$  consecutive days, at any time after initial confirmatory results
- ALT and/or AST are  $>8$  x ULN

In each of these situations, study medication will be discontinued, the Sponsor notified and the End of Treatment Visit performed within 3 days of the confirmed laboratory results (see Section 5.8.1). At the End of Treatment Visit, medical history including details of risk factors for liver diseases (if not previously assessed) will be requested and additional blood sampling performed (**Specialized Liver Panel** and **Liver Discontinuation Panel**, see detailed below). Patient should also be scheduled for a Follow-up Visit (ie, procedures of Visit 18) 3 weeks

after discontinuation of investigational product. A referral consultation to a hepatologist or gastroenterologist (specializing in liver abnormalities) should be obtained.

Any additional tests and/or examinations should be carried out at the discretion of the Investigator. Any further investigations and laboratory results for patients with abnormal laboratory values at the Follow-up Visit should be made available to the Sponsor upon request.

Additional information, including but not limited to completion of supplemental eCRFs may be requested for certain adverse events and/or laboratory abnormalities which are reported/identified as part of the hepatic safety surveillance.

Following the End of Treatment Visit, the Investigator should continue to monitor the subject's liver tests every 3 days following receipt of the prior laboratory results until the ALT and AST are  $\leq 2$  x ULN or until ALT and AST are at or below baseline levels. The frequency of retesting can decrease to once a week or less if abnormalities stabilize and the subject is asymptomatic.

### **Guidance on Assessment of Hepatic Laboratory Abnormalities**

The following is presented to assist in the evaluation and management of hepatic laboratory values. It is not intended to supplant Investigators' clinical judgment.

Patients who experience ALT and/or AST values  $>3$  x ULN confirmed with a repeated test will have the following performed within 3 days of the confirmed laboratory results:

- AE assessment
- Physical Examination for jaundice and other signs of liver diseases
- Review of relevant risk factors and current history focusing on possible causes of the increased ALT and/or AST and/or TB, including:
  - Use of suspect concomitant medication [including over-the-counter (ie, acetaminophen/paracetamol), herbal and vitamin preparations]
  - Recent alcohol consumption or recreational drug/narcotic use
  - Recent unaccustomed physical exertion
  - Occupational or environmental exposure to hepatotoxins
  - Other conditions which may cause liver diseases or which may cause abnormal test results
- Specialized Liver Laboratory Panel (see below)

### **Specialized Liver Panel**

For patients who are being monitored frequently as a result of confirmed AST and/or ALT >3X ULN, additional central laboratory tests will be performed within 3 days of receipt of confirmatory results. These laboratory tests will study the possible causes of the increased ALT and/or AST and/or TB, and may include, but are not limited to, the following tests:

- Hepatitis A IgM
- Hepatitis BsAg
- Hepatitis B Core Ab IgM
- Hepatitis C virus RNA
- Hepatitis C Ab
- Hepatitis E IgM
- Epstein-Barr Virus (EBV) IgM Ab
- Lactate Dehydrogenase (LDH)
- Gamma-glutamyl-transpeptidase (GGT)
- Carbohydrate deficient transferrin (CDT)
- Prothrombin time (PT/INR)
- Iron Panel - iron, ferritin, total iron binding capacity (TIBC)
- Immunology Panel including Antinuclear Antibody (ANA), Anti-Smooth Muscle Antibody (SMA) and Anti-Liver/Kidney Microsomal Antibody (Anti-LKM)
- Anti-tissue Transglutaminase Antibody

### **Liver Discontinuation Panel**

[figure not shown]
For patients who are discontinued from the study as a result of sustained elevated liver safety abnormalities, additional central laboratory tests will be performed at the time of End of Treatment Visit. Similar to the Specialized Liver Panel, these laboratory tests will study the possible causes of the increased ALT and/or AST and/or TB, and may include, but are not limited to, the following tests:

- Cytomegalovirus (CMV) IgM Ab
- Herpes Simplex Virus (HSV) 1 and 2

- Ceruloplasmin
- Toxoplasmosis
- Alpha-1 antitrypsin

For specific details regarding the Specialized Liver Panel or the Liver Discontinuation Panel laboratory tests, refer to the Central Laboratory Manual for this study.

**Figure 1 Sustained elevated liver safety abnormalities flow chart**

a In patients with repeat ALT or AST > 3X ULN but ≤ 8X ULN, only patients with TB ≤ 1.5X ULN at Step 1 should be followed according to Step 2b. Patients with an initial TB and confirmatory repeat TB > 1.5X ULN should be followed according to Step 2d.

b Please see text above in the Appendix for details on additional assessments to be performed (AE assessment, PE, review of current medical history including focused review of risk factors for liver diseases and collection of blood samples [specialized liver panel or liver discontinuation panel]).

c Confirmatory repeat AST, ALT, ALK-P and TB should be obtained every 3 days following receipt of prior laboratory results, until the ALT and AST are ≤ 2X ULN or until ALT and AST are at or below baseline levels. The frequency of retesting can decrease to once a week or less if abnormalities stabilize and the patient is asymptomatic.

---

## **CASE IDENTIFICATION AND MANAGEMENT OF DECREASED RENAL FUNCTION**

In order to standardise the definition and management of decreased renal function, the following guideline has been developed. Please note separate sections for patients who are treated with metformin and for those who are not treated with metformin (eg, Section 5.8 CSP).

### **FOR PATIENTS WHO ARE TREATED WITH METFORMIN:**

If calculated creatinine-clearance is  $<60$  ml/min or if there is an increase in serum creatinine of  $\geq 0.5$  mg/dL ( $\geq 44.2$   $\mu\text{mol/L}$ ) above the baseline value based on central laboratory results, this will be considered a case of “decreased renal function”.

In this circumstance, the investigator should consider evaluating the patient for potentially reversible causes of renal dysfunction including:

1. concurrent use of NSAIDs, antibiotics, or other medications known to affect measures of serum creatinine
2. volume depletion
3. urinary tract infection
4. obstructive uropathy.

Patients should return for repeat central laboratory testing as soon as possible, no later than 7 days after the abnormal result. Investigational drug and metformin should be interrupted pending the results of repeat testing. If after interruption creatinine-clearance is still  $<60$  ml/min or if the serum creatinine value remains  $\geq 0.5$  mg/dL ( $\geq 44.2$   $\mu\text{mol/L}$ ) above the baseline value, the patient should permanently discontinue the study medication and be withdrawn from the study (in which case an Adverse Event must be reported).

If after interruption of investigational drug and metformin creatinine-clearance is  $\geq 60$  ml/min or if the serum creatinine value has decreased to  $<0.5$  mg/dL ( $<44.2$   $\mu\text{mol/L}$ ) above baseline, investigational drug and metformin can be re-started if appropriate in the judgement of the investigator and following consultation with the study team physician. If the patient restarts investigational drug and metformin and creatinine-clearance is again  $<60$  ml/min or the serum creatinine value increases again to  $\geq 0.5$  mg/dL ( $\geq 44.2$   $\mu\text{mol/L}$ ) above baseline, the patient should permanently discontinue the study medication and be withdrawn from the study (in which case an Adverse Event must be reported).

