### **Development of any study specific criteria for discontinuation:**

8. Treatment with glucocorticoids equivalent to oral prednisolone >10 mg/day (two temporary periods of higher daily doses for no longer than 7 days each are allowed)
9. Major and/or frequent hypoglycaemic events, defined as  $\geq 1$  major event or recurring minor events (See 6.4.9.1 for definition of minor and major). This definition should be applied after possible contributing factors (eg, excessive physical activity) have been excluded by the investigator

10. Pregnancy confirmed by a positive pregnancy test or otherwise verified
11. Change in kidney function (Please see [Appendix K](#) for further guidance):
  - For all patients treated with metformin: calculated creatinine-clearance <60 mL/min or an increase in serum creatinine of  $\geq 44 \mu\text{mol/L}$  ( $\geq 0.5 \text{ mg/dL}$ ) above the baseline value confirmed by a repeated measurement within one week.
  - For patients not treated with metformin: a) calculated creatinine clearance <60 ml/min or b) in subjects with baseline creatinine  $\geq 123 \mu\text{mol/L}$  ( $\geq 1.4 \text{ mg/dL}$ ) an absolute increase in serum creatinine of  $\geq 88 \mu\text{mol/L}$  ( $\geq 1.0 \text{ mg/dL}$ ), or c) in subjects with baseline creatinine <123  $\mu\text{mol/L}$  (<1.4 mg/dL) an absolute increase in serum creatinine of  $\geq 44 \mu\text{mol/L}$  ( $\geq 0.5 \text{ mg/dL}$ ).
12. CK >10x ULN confirmed at a repeated measurement preferably within 24 hours, but not exceeding 72 hours, see Section [5.8.1](#)
13. Patients with a central laboratory ALT and/or AST >3x ULN will be scheduled for a follow-up visit within 3 days following the receipt of the result. See [Appendix J](#) for further guidance. Patients should be discontinued from treatment if the initial **and** repeated laboratory tests meet any of the following criteria:
  - ALT and/or AST are >3x ULN **and** TB>1.5x ULN
  - ALT and/or AST are >5x ULN for  $\geq 14$  consecutive days, at any time after initial confirmatory results
  - ALT and/or AST are >8x ULN.
14. Serum Sodium  $\leq 125 \text{ mmol/L}$  with or without symptoms; see [Appendix I](#) for further guidance

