### **FOR PATIENTS WHO ARE NOT TREATED WITH METFORMIN:**

If a) calculated creatinine clearance is  $<60$  ml/min or b) in subjects with baseline creatinine  $\geq 123$   $\mu\text{mol/L}$  ( $\geq 1.4$  mg/dL) an absolute increase occurs in serum creatinine of  $\geq 88.4$   $\mu\text{mol/L}$

( $\geq 1.0$  mg/dL) above the baseline value based on central laboratory results, or c) in subjects with baseline creatinine  $< 123$   $\mu\text{mol/L}$  ( $< 1.4$  mg/dL) an absolute increase occurs in serum creatinine of  $\geq 44.2$   $\mu\text{mol/L}$  ( $\geq 0.5$  mg/dL) above the baseline value based on central laboratory results, this will be considered a case of “decreased renal function”.

In this circumstance, the investigator should consider evaluating the patient for potentially reversible causes of renal dysfunction including:

1. concurrent use of NSAIDs, antibiotics, or other medications known to affect measures of serum creatinine
2. volume depletion
3. urinary tract infection
4. obstructive uropathy.

Patients should return for repeat central laboratory testing as soon as possible, no later than 7 days after the abnormal result. Investigational drug should be interrupted pending the results of repeat testing. If after interruption creatinine-clearance is still  $< 60$  ml/min or if the serum creatinine value remains either  $\geq 88.4$   $\mu\text{mol/L}$  ( $\geq 1.0$  mg/dL) or  $\geq 44.2$   $\mu\text{mol/L}$  ( $\geq 0.5$  mg/dL) above the baseline value, respectively, the patient should permanently discontinue the study medication and be withdrawn from the study (in which case an Adverse Event must be reported).

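### Appendix K joins both the renal stop rule and the restart rule with *or*, so a patient who crossed both limits and recovered on one is told to stop permanently and may also be restarted

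*Supplement*

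**What the plan says.** Appendix K opens by stating its purpose: "In order to standardise the definition and management of decreased renal function". It then gives two parallel procedures, one for patients on metformin and one for patients not on it.

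In the metformin part, a case is a calculated creatinine clearance below 60 ml/min or a serum creatinine rise of at least 0.5 mg/dL over baseline. Study drug and metformin are interrupted and the tests repeated within 7 days. Two rules then apply:

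- **Stop.** Clearance still below 60 "ml/min or if the serum creatinine value remains" at least 0.5 mg/dL above baseline: "the patient should permanently discontinue the study medication and be withdrawn from the study".
- **Restart.** Clearance at least 60 "ml/min or if the serum creatinine value has decreased to" less than 0.5 mg/dL above baseline: study drug and metformin "can be re-started if appropriate in the judgement of the investigator and following consultation with the study team physician".

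A third sentence covers restarted patients. If clearance is again below 60 "ml/min or the serum creatinine value increases again to" the limit, they stop permanently.

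The non-metformin part is built the same way. Its rise limit is 1.0 mg/dL when baseline creatinine is at least 1.4 mg/dL, and 0.5 mg/dL otherwise. The stop condition is clearance still below 60 "ml/min or if the serum creatinine value remains either" applicable limit, and the restart condition is again joined by *or*.

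Protocol Section 5.8, item 11, lists either criterion alone as a ground for discontinuation ("For all patients treated with metformin: calculated creatinine-clearance <60 mL/min or an increase in serum creatinine of" at least 0.5 mg/dL, confirmed on repeat) and refers to Appendix K for further guidance.

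**The concern.** The stop and restart rules are meant to divide patients at the repeat test into those who come off for good and those who may resume. They do that only if one condition is the negation of the other. Negating *A or B* gives *not A and not B*, but the restart sentence says *not A or not B*. A patient with one measure still abnormal and the other recovered falls under both sentences.

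At stake is the consistency of a safety stopping rule. For the same laboratory result, one site may withdraw the patient and another may re-expose the patient to study drug and, in the metformin part, to metformin as well. A patient restarted with clearance still below 60 would meet the clearance threshold of the re-breach sentence at the next test with no further change.

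**Working it through.** **1. The logic.** Status at the repeat test:

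| Clearance | Creatinine rise | Stop (*or*) | Restart as written (*or*) | Restart with *and* |
|---|---|---|---|---|
| recovered | recovered | no | yes | yes |
| recovered | not recovered | yes | yes | no |
| not recovered | recovered | yes | yes | no |
| not recovered | not recovered | yes | no | no |

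Two of the four states overlap as written, and none overlaps with *and*.

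**2. A more charitable reading.** One can tie each clause to the limit that the patient originally crossed. Then someone who crossed only the creatinine limit is judged only on creatinine, and the conflict disappears for that patient. It does not disappear for a patient who crossed both limits: one value is still abnormal while the other has come down. The rest of the check uses only such patients.

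**3. Whether the mixed state can occur.** Section 11.2.2 specifies the Cockcroft-Gault formula. With weight and age constant, clearance is inversely proportional to creatinine:

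clearance(s) = C0 × s0 / s,

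where C0 and s0 are baseline clearance and creatinine. Clearance equals 60 at s_c = s0 × C0 / 60. The rise limit L is reached at s_r = s0 + L. A patient whose first value lies beyond both s_c and s_r, and whose repeat lies between them, has recovered on one measure only.

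Baseline values are assumed. Each is eligible, because Section 4.2 (criterion 12) excludes only clearance below 60.

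| Case | C0; s0; L | First test | Repeat test | Stop by | Restart by |
|---|---|---|---|---|---|
| 1 | 80; 1.0; 0.5 | 1.6: 80/1.6 = 50.0, rise 0.6 | 1.4: 80/1.4 = 57.1, rise 0.4 | clearance | creatinine |
| 2 | 100; 1.0; 0.5 | 1.8: 100/1.8 = 55.6, rise 0.8 | 1.6: 100/1.6 = 62.5, rise 0.6 | creatinine | clearance |
| 3 (no metformin) | 80; 1.4; 1.0 | 2.5: 112/2.5 = 44.8, rise 1.1 | 2.2: 112/2.2 = 50.9, rise 0.8 | clearance | creatinine |

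In case 3, C0 × s0 = 80 × 1.4 = 112. With *and* in the restart rule, all three cases are stop only.

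**4. Width of the overlap**, for patients whose first value crossed both limits:

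| C0; s0; L | s_c | s_r | Repeat values in conflict (mg/dL) |
|---|---|---|---|
| 70; 1.0; 0.5 | 1.17 | 1.50 | 1.17–1.50; restart open at clearance 46.7–60 |
| 80; 1.0; 0.5 | 1.33 | 1.50 | 1.33–1.50; restart open at clearance 53.3–60 |
| 90; 1.0; 0.5 | 1.50 | 1.50 | no interval; the limits coincide |
| 100; 1.0; 0.5 | 1.67 | 1.50 | 1.50–1.67; restart open at rise 0.50–0.67 |
| 80; 1.4; 1.0 | 1.87 | 2.40 | 1.87–2.40; restart open at clearance 46.7–60 |

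The limits coincide at C0 = 60 × (1 + L/s0). That is 90 for s0 = 1.0 and L = 0.5, and 102.9 for s0 = 1.4 and L = 1.0. Below that baseline clearance the unsafe direction applies: restart is open with clearance still under 60.

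**5. A full Cockcroft-Gault example.** Take a man of 80 kg and 70 years with baseline creatinine 1.0. His clearance is 80 × (140 − 70) / (72 × 1.0) = 77.8. At creatinine 1.5 it is 51.9 with a rise of 0.5, so both limits are crossed. At a repeat value of 1.4 it is 55.6 with a rise of 0.4, so both sentences apply.

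**The case against.** The best case against is that the protocol as a whole already answers the question.

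- Section 3.2.4 says that, for patients not on metformin, study drug discontinuation will occur on any one of the listed limits, and that metformin must be discontinued below 60 or at a confirmed rise. Section 5.8, item 11, also treats either criterion as sufficient.
- Section 5.2 bars withdrawn patients from re-entering, and the stop sentence requires withdrawal.
- Stop is directive and restart is permissive. Restart needs investigator judgement and consultation with the study team physician, and the re-breach sentence is a backstop.
- The group is small, and nothing inferential depends on it. On this view it is a drafting slip.

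Much of this stands. The intent to stop on either limit is clear, the safeguards limit harm, and the cause is probably a slip. The word for recurrence in the re-breach sentence points the same way, since it presupposes that the value had recovered.

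It does not remove the conflict. Sections 3.2.4 and 5.8 both refer to Appendix K, and neither says which of its two sentences prevails. The bar on re-entry applies only once withdrawal has been carried out, and whether to withdraw is the open question. The consulted physician reads the same two sentences. The evidence of intent shows which word is wrong, and the wrong word remains in an operative safety rule.

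**Conclusion.** The point holds and should be fixed. In both parts of Appendix K the restart condition is not the complement of the stop condition. The conflict survives even when each criterion is applied only to patients who crossed it. On a fully literal reading it is wider and takes in any patient with exactly one criterion abnormal at the repeat, but the conclusion does not need that.

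The size is shown by illustration only. At baseline creatinine 1.0 mg/dL and baseline clearance 70 to 80 ml/min, restart is open at clearances from about 47 or 53 up to 60. These figures assume constant weight and age and invented baseline values. The documents give no frequency of such patients and none is claimed. The group is narrow, and other texts favour stopping. The amendment log lists changes to Appendices E and J but none to Appendix K, so the wording is current.

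**What to change.** In both parts of Appendix K, make the restart condition read: clearance at least 60 ml/min **and** creatinine rise below the applicable limit. Restart is then the exact complement of the stop rule. It also agrees with Section 5.8, item 11, with Section 3.2.4, and with the re-breach sentence.

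The cost is one word in each of two sentences at the next amendment, plus a notification to sites. Sample size, power, alpha and analysis sets are unchanged.
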